7.8.3 Vital signs

For vital signs (blood pressure and pulse rate), descriptive statistics including change from baseline will be calculated by dose group and by planned time point based on the last value of the subject at that planned time point (or assigned to that planned time point). In the listing the difference from baseline will also be displayed.

Descriptive statistics over time will also be provided for the orthostatic test results (SRD part only) to enable checking of orthostatic hypotension occurrence. Subjects should have spent at least 5 min in the supine position before blood pressure and pulse rate will be measured the first time. Further 2 measurements will be performed immediately after standing up and after 3 min in a standing position. An orthostatic hypotension is defined as a decline in systolic blood pressure of ≥ 20 mmHg or a decline in diastolic blood pressure of ≥ 10 mmHg within the first three minutes after standing up.

Clinically relevant findings in vital signs will be reported as AEs.

7.8.4 ECG**Continuous safety ECG monitoring (by investigator)**

Clinically relevant abnormal findings will be reported as adverse events.

No separate listing or analysis of continuous ECG monitoring will be prepared.

12-lead ECG

Abnormal findings will be reported as baseline conditions (at screening) or as AEs (during the trial) if judged clinically relevant by the investigator.

All evaluations of ECG data (SRD part only) will be based on the TS, except the exposure-response analyses, which are based on the ECGPCS set.

Listing of individual data

For all quantitative endpoints, listings of individual data will be shown in Appendix 16.2. For QTcB and RR, only listings will be provided. Occurrences of notable findings will be flagged.

Comments regarding the ECGs will be listed.

Categorical endpoints

For the categorical endpoints, frequency tables will be provided.

Categorical endpoints will also include morphological findings that might be attributable to treatment. In particular, new onsets of findings not present at baseline will be explored. A morphological finding observed on treatment that was not reported at baseline will be categorized as a ‘new onset’ of this finding.

For all subjects with any notable finding in ECG intervals, a separate listing will be created as end-of-text display (based on the same display template as in Appendix 16.2), and the corresponding time profiles will be shown.

Quantitative endpoints

Descriptive statistics (N, mean, SD, min, median, max) will be provided for the absolute values and changes from baseline over time of QTcF, HR, QT, PR and QRS. The time profiles of mean and SD for the changes from baseline on treatment will be displayed graphically by treatment.

For QTcF and HR changes from baseline, the relationship to the corresponding plasma concentrations will be evaluated using a random coefficient model. For subjects in the ECGPCS, all time points with available ECG endpoints and valid time-matched drug plasma concentrations will be included. For the handling of missing values, see [Section 6.6](#).

The response variable will be the change from baseline in QTcF (Δ QTcF). The placebo subjects will be included in the analysis, setting their plasma concentrations to zero.

As a first step, it is investigated if there is a potential delayed or accelerated (e.g. due to metabolites) effect of the drug on QTcF. A general visual impression will be provided by overlaying time profiles of plasma concentrations and QTcF changes from baseline (Δ QTcF). These figures will be generated for each subject (presented in the Statistical Appendix of the CTR), as well as for means per treatment group (presented in the End-of-Text part of the CTR).

The relationship between BI 474121 plasma concentrations and QTcF changes from baseline will be investigated in an exploratory manner using a random coefficient model to estimate the difference in means between BI 474121 and placebo of QTcF change from baseline and its 90% confidence interval at the geometric mean of C_{max} for each dose. Additionally, the estimated overall slope with its 90% confidence interval will be provided. The used random coefficient model is based on a white paper from Garnett et. al. (14) with Δ QTcF as response variable, centered baseline QTc and plasma concentration as continuous covariates and treatment as fixed categorical effects, and a random intercept and slope for each subject. Restricted maximum likelihood estimation will be performed, and the Kenward-Roger method will be applied to adjust standard errors and estimate denominator degrees of freedom. For more details refer to [Section 10.1.4](#).

For visualization, a scatterplot of the BI 474121 plasma concentration against the following individual QTcF values will be provided: For each subject on active treatment and each time point, subtract the mean value of all individual observed Δ QTcF values from the placebo group for this time point from the individual observed Δ QTcF value for this subject and time point. This results in estimates for “individual $\Delta\Delta$ QTcF” values, which should only be used for plotting purposes. The corresponding regression line and its pointwise confidence bands as well as and the geometric means of C_{max} for each dose will additionally be displayed in the plot.

The goodness of fit of the above model will be checked. The visual checks will include the inspection of concentration-QTcF quantile plots (14) and residual plots. In case of non-linearity or if there is evidence for a delayed effect, further models will be explored in order to better characterise the PK-ECG relationship.

All of the above described graphical and statistical analyses will be also performed for HR in place of QTcF.

Appropriateness of heart rate correction methods of QT interval

To evaluate the appropriateness of the heart rate correction methods, the slope of the relationship of QTcF interval versus RR interval will be estimated separately for off-drug values and active treatment, by applying the random coefficient model described in [Section 10.1.2](#) using the QTcF and RR variable values per time point. A scatterplot of QTcF vs RR including the overall regression lines will be included in the Statistical Appendix of the CTR.

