6.7 BASELINE, TIME WINDOWS AND CALCULATED VISITS

SRD part: The baseline value is defined as the last measurement before first administration of trial medication (BI 474121 or Placebo).

BA part: The baseline value is defined as the last measurement before administration of trial medication in each treatment period (e.g. ptm -2:00).

For laboratory analysis, the last value on treatment will be defined as the last value during corresponding treatment period (usually 96:00h in first and second treatment period).

Adherence to time windows will be checked via the consistency check listings at the RPM.

Unscheduled measurements of laboratory data and vital signs data will be assumed to be repeat measurements of the most recent scheduled measurement (e.g. for follow-up or confirmation of a particular value). Therefore, unscheduled measurements will be assigned to the planned time point of the previous scheduled measurement.

There will be a centralised evaluation of the 12-lead ECG recordings of the SRD part at the time points and for the ECG recordings specified in [Table 6.7: 1](#) below:

Table 6.7: 1 Time schedule of 12-lead ECG recordings (SRD part)

Visit	Day	Planned time [hh:mm] (relative to drug administration)	Study phase	Central evaluation
1	-21 --1		Screening	NA
2	1	-01:00	Baseline	first ECG of each of the 3 triplicate baselines
		-00:45		
		-00:30		
		00:30		
		01:00		
		01:30		
		02:00		
		03:00		
		04:00		
		06:00		
		08:00		
		12:00		
	2	24:00		
		34:00		
	3	48:00	On-treatment	first single ECG of the triplicate
	4	72:00		
	5	96:00		
5	8-15		End-of-study examination	NA

At Screening and End-of-study examination ECG recordings are performed as single ECGs and will not be transferred to central ECG lab. Three triplicate ECGs will be recorded as the baseline before the first drug administration, but only the first ECG of each of the 3 baseline triplicates will be transferred to the database. At all other time points, 1 triplicate ECG will be recorded, but only the first single ECG of the triplicate will be transferred to the database. The baseline value of an ECG variable is defined as the mean of the ECG variable values prior to drug administration.

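### The visual check for a delayed QTcF effect uses change from a pre-dose baseline without placebo correction, so time-of-day or meal changes shared with placebo can mimic or mask a delay

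*SAP*

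**What the plan says.** SAP Section 7.8.4 (quantitative ECG endpoints) opens the concentration-QTcF work with a timing check: "As a first step, it is investigated if there is a potential delayed or accelerated" effect of the drug on QTcF. The tool is graphical: "A general visual impression will be provided by overlaying time profiles of plasma concentrations and QTcF changes from baseline". The figures are drawn for each subject "as well as for means per treatment group".

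SAP Section 6.7 fixes what change from baseline means here: "The baseline value of an ECG variable is defined as the mean of the ECG variable values prior to drug administration". Table 6.7: 1 puts those readings at 1:00, 0:45 and 0:30 before dosing.

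For the scatterplot against concentration, Section 7.8.4 defines a placebo-corrected value: "For each subject on active treatment and each time point, subtract the mean value of all individual observed" changes on placebo at that time point from the subject's own change. These are values "which should only be used for plotting purposes".

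The goodness-of-fit paragraph then says: "In case of non-linearity or if there is evidence for a delayed effect, further models will be explored". The visible text does not say what counts as evidence of delay, or that it is judged against placebo. Section 7.8.4 applies the same graphs and models to HR.

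**The concern.** The overlay is the named figure for judging effect against time, and the quantity plotted mixes two time courses. One is the drug effect. The other is whatever QTcF does between early morning and evening, including around meals, in people who received no drug. Baseline falls at about 07:00 to 07:30, while Day 1 ECGs run from about 08:30 to 20:00. Lunch follows the 4 h recordings, a voluntary snack comes at 8 h and dinner at 10 h (Protocol Flow Chart, SRD part). Baseline is not matched by clock time, so it does not remove this second component.

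A direct effect could therefore look delayed and prompt extra models chosen after seeing the data. A real delay could also be flattened by an opposite daily change and leave a direct-effect model unquestioned. The correction that separates the two is already defined in the same section but is used where time is not displayed.

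**Working it through.** The plan states no figure for this check, so there is none to reproduce.

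**Structure.** Let s(t) be the QTcF pattern shared by all subjects, s(b) its value at baseline and d(t) the drug effect.

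- Active mean change: d(t) + s(t) − s(b)
- Placebo mean change: s(t) − s(b)
- Active minus placebo: d(t)

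The uncorrected overlay compares concentration with the first line; only the third has the drug's own timing.

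**Inputs from the documents.** Half-life 18.6 h (Protocol 1.4.3); ECG times from SAP Table 6.7: 1; 6 active per dose and 2 × 7 = 14 placebo (Protocol 3.1).

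**Assumptions, not in the documents.** One-compartment oral kinetics with absorption rate 2 per h (tmax about 2 h); direct effect of 5 ms at Cmax; shared 24 h cosine of amplitude 2 ms peaking at 20:00; baseline taken at 07:15.

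**Apparent delay, without noise.** Concentration relative to peak is 1.00 at 2 h and 0.70 at 12 h. The shared term is 2 × [cos(15° × (clock − 20)) − cos(15° × (7.25 − 20))], and the baseline cosine is −0.981.

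| Time | Drug effect | Shared change | Uncorrected | Corrected |
|---|---|---|---|---|
| 2 h (10:00) | 5 × 1.00 = 5.0 | 2 × (−0.866 + 0.981) = 0.2 | 5.2 ms | 5.0 ms |
| 12 h (20:00) | 5 × 0.70 = 3.5 | 2 × (1 + 0.981) = 4.0 | 7.5 ms | 3.5 ms |

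The uncorrected profile is highest at 12 h although the effect is direct.

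**Masking, without noise.** Move the cosine peak to 08:00, so the shared change is −0.2 ms at 2 h and −4.0 ms at 12 h. Suppose a truly delayed effect of 2 ms at 2 h and 5 ms at 12 h (assumed). Uncorrected values are 2 − 0.2 = 1.8 ms and 5 − 4.0 = 1.0 ms, so the later, larger effect appears smaller.

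**With noise: amplitude.** Absorption rate 1 per h (scheduled tmax 3 h), 5 ms direct effect, 20:00 peak, residual SD 8 ms, 6 active and 14 placebo. The table gives the share of simulated dose-group means that peak at least 2 h after tmax.

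| Shared amplitude | Uncorrected | Corrected |
|---|---|---|
| 0 ms | 36% | 36% |
| 2 ms | 65% | 37% |
| 4 ms | 88% | 39% |
| 6 ms | 97% | 37% |

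**With noise: phase.** tmax 2 h, 10 ms direct effect, amplitude 5 ms, residual SD 7 ms, peak counted as late at 4 h or later. The uncorrected share is 5% for a 04:00 daily peak, 7% for 08:00, 33% for 12:00, 80% for 16:00, 95% for 20:00 and 68% for midnight. The average over these six is 288/6 = 48%. The corrected share is about 35% in every case.

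**Cost in precision.** The SE ratio for a dose-group mean is √(1/6 + 1/14) / √(1/6) = √(1 + 6/14) = 1.195, about 20% more.

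**The case against.** A reader might infer that this overlay decides whether the direct-effect model stands, and that an apparent delay would replace it. The documents do not support that. The overlay is offered as a general impression. The phrase about evidence of delay comes later, after quantile and residual plots have been named, and the result is that further models are explored within an analysis described as exploratory. No text withdraws the planned model or its reported slope and intervals.

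A placebo reference also exists. Section 7.8.4 plots mean change profiles by treatment, and the treatment-group overlays do not exclude placebo, so a shared pattern could be discounted by eye. The SAP does not require that comparison, and a single active subject's overlay contains no placebo curve. The quantile plots are against concentration, and no residual plot against time is named.

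The percentages could also be misread as expected error rates. They are not. The time of the highest mean is a metric the SAP does not use; the SAP looks at whole profiles, with ECGs to 96 h. That metric flags delay in roughly 35–40% of groups from noise alone, before and after correction. With the assumed 2 per h absorption, concentration at 4 h is still 95% of peak, so a maximum there is weak evidence of anything. Phase alone moves the uncorrected figure from 5% to 95%.

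Finally, Section 7.8.4 refers to Section 10.1.4 for model details, and Section 10 is not in the available text. A delay rule or time term there cannot be excluded. A time term in the model would not by itself change what this overlay shows.

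**Conclusion.** The point holds as a limited one. The first-step check plots a quantity that contains any time-of-day or meal pattern shared with placebo, and nothing visible requires delay to be judged against placebo. The direction follows from the algebra and needs no simulation: a shared pattern can create or hide an apparent delay, and subtracting the placebo mean removes it in expectation. How large the distortion would be in this trial is unknown, because it rests on an assumed amplitude and phase.

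Severity is optional to minor. The check feeds an exploratory analysis with other diagnostics beside it, and no dose decision depends on it: cardiac safety during the study uses the site's ECG readings, and the central evaluation is done post-study (Protocol 5.2.5.1). The case for acting is that a less biased figure is almost free.

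**What to change.** In SAP 7.8.4, keep the planned overlays, including those for placebo and the raw subject profiles. Add overlays of concentration with the placebo-corrected change already defined for the scatterplot, primarily as dose-group means, and state that evidence for a delayed effect is judged on these. Do the same for HR. The existing limit to plotting is no obstacle, since the overlay is a plot. Adding is better than replacing, because the corrected value is defined only for subjects on active treatment and replacement would remove the placebo and uncorrected subject profiles.

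Cost: a sentence in the SAP, one more set of figures, no new data, and an SE about 20% higher for each corrected dose-group mean.

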		8:00	16:00	Snack (voluntary) ³		x	+		x	x		x
		10:00	18:00	Dinner ³		x						
		12:00	20:00			x	+		x		x	x
	2	24:00	08:00	Breakfast ³	x ^B	x	+		x		x	x
		29:00	13:00	Lunch ³								x
		32:00	16:00	Snack (voluntary)								
		34:00	18:00	Dinner ³		x			x		x	x
	3	48:00	08:00	Breakfast (voluntary) ³ , confirmation of fitness and discharge from trial site		x		▼	x		x	x
	4	72:00	08:00	Ambulatory visit	x ^B	x			x		x	x
	5	96:00	08:00	Ambulatory visit		x			x		x	x
5	8- 15			End of trial (EoTrial) examination ⁴	x ^D				x		x	x

1. Subject must be informed and written informed consent obtained prior to starting any screening procedures. Screening procedures include physical examination, check of vital signs, ECG, 12-lead ECG and rhythm strip over at least 15 min, safety laboratory (including drug screening), demographics (including determination of body height and weight, smoking status and alcohol history, relevant medical history, concomitant therapy and review of inclusion/exclusion criteria. Pharmacogenetic samples will be collected if needed.
2. The time is approximate; procedures are to be performed and completed within the 3 h prior to drug administration. Allocation to treatment may be performed at any time following enrolment but must be completed prior to (first) drug administration.
3. If several actions are indicated at the same time, the intake of meals will be the last action.
4. At the end of trial visit the EoTrial examination includes physical examination, vital signs, ECG, safety laboratory, recording of AEs, and concomitant therapies.
5. Includes urine drug screening and alcohol breath test at this time.
6. AEs and concomitant therapies will be recorded throughout the trial, but will be specifically asked for at the times indicated in the Flow Chart above.

Proprietary confidential information © 2020 Boehringer Ingelheim International GmbH or one or more of its affiliated companies

7. Safety laboratory to be taken and to be medically evaluated within 74 h prior to administration of study drug; this safety laboratory assessment can be omitted if the screening examination is performed on Days -3, -2 or -1.
8. One blood sample for stability testing will be taken at this time (refer to Section [5.3.2.4](#))
9. Letters A, B, C, D and E describe different sets of safety laboratory examinations (see Table [5.2.4: 1](#)).

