6. GENERAL ANALYSIS DEFINITIONS

6.1 TREATMENTS

For basic study information on investigational products, assignment of treatment, please see CTP, Sections 3 and 4.

The SRD part is designed as single-blind within dose groups, randomised, and placebo-controlled within parallel dose groups. It is planned to include 56 healthy male subjects in this part of the trial. The subjects will be assigned to 7 groups consisting of 8 subjects per group (6 subjects will receive BI 474121 and 2 will receive placebo).

The BA part will be performed as randomised, open-label, three-way, six-sequence, crossover trial in healthy male subjects. It is planned to include 12 healthy male subjects. The subjects will be randomly allocated to the 6 treatment sequences. There will be a wash out period of at least 7 days between the treatments.

For details see Table 6.1:1 and [Table 6.1:2](#) below.

Table 6.1: 1 Treatments and labels used in the analysis – SRD part

Treatment	Label in dataset	Short label
P*	Placebo, solution, po, qd	Plc os
Q*	Placebo, tablet, qd	Plc tab
A	BI 474121, 0.5 mg/mL solution, 0.25 mg, po, qd	BI 0.25mg os
B	BI 474121, 0.5 mg/mL solution, 1.0 mg, po, qd	BI 1mg os
C	BI 474121, tablet, 2.5 mg, po, qd	BI 2.5mg tab
D	BI 474121, tablet, 2*2.5 mg, po, qd	BI 5mg tab
E	BI 474121, tablet, 10 mg, po, qd	BI 10mg tab
F	BI 474121, tablet, 2*10 mg, po, qd	BI 20mg tab
G	BI 474121, tablet, 4*10 mg, po, qd	BI 40mg tab

*: Each placebo group in the safety evaluation will consist of all placebo treated patients in SRD part, regardless of the dose group in which they were treated.

Table 6.1: 2 Treatments and labels used in the analysis – BA part

Treatment sequence	Short label in dataset	Short label
UVW	BI 474121 10 mg solution / tablet fasted / tablet fed	R/T2/T1
UWV	BI 474121 10 mg solution / tablet fed / tablet fasted	R/T1/T2
VUW	BI 474121 10 mg tablet fasted / solution / tablet fed	T2/R/T1
VWU	BI 474121 10 mg tablet fasted / tablet fed / solution	T2/T1/R
WUV	BI 474121 10 mg tablet fed / solution / tablet fasted	T1/R/T2
WVU	BI 474121 10 mg tablet fed / tablet fasted / solution	T1/T2/R

U=R (Reference treatment)

V=T2 (Test treatment 2)

W=T1 (Test treatment 1)

The short label will be used whenever tables/listings are displayed by treatment sequence. If actual treatment is shown the following labels will be used: BI 10mg tab fed, BI 10mg tab fasted, BI 10mg solution (e.g. AE tables).

Section 1.2.6 of CTP:

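### The listed concentration-QTcF model (also used for HR) has no time term, so a daily change shared with placebo can bias the slope and the higher-dose differences

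*SAP*

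**What the plan says.** SAP Section 7.8.4 takes the QTcF change from baseline as the response and names the other terms: "centered baseline QTc and plasma concentration as continuous covariates and treatment as fixed categorical effects, and a random intercept and slope for each subject". Estimation is by REML with the Kenward-Roger adjustment, and the reader is sent to Section 10.1.4 for more. The public text goes from Section 9 to Section 11, so 10.1.4 cannot be read.

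Four other provisions matter here:

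- **Placebo.** "The placebo subjects will be included in the analysis, setting their plasma concentrations to zero".
- **Baseline.** SAP Section 6.7: "The baseline value of an ECG variable is defined as the mean of the ECG variable values prior to drug administration". Table 6.7: 1 puts these recordings at 1:00, 0:45 and 0:30 before dosing.
- **Heart rate.** "All of the above described graphical and statistical analyses will be also performed for HR in place of QTcF".
- **Treatment coding.** 7.8.4 does not say whether treatment is active versus placebo or one level per dose. The labels in SAP Table 6.1: 1 are by dose, for example "BI 474121, tablet, 4*10 mg, po, qd".

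The model yields the overall slope, and the active-minus-placebo difference at the geometric mean Cmax of each dose, each with a 90% CI. For the scatterplot only, the placebo mean at each time point is subtracted from the active values.

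**The concern.** The SRD flow chart schedules dosing at about 08:00, and all post-dose ECG times are pooled. Within an active subject, concentration is therefore a function of time after dose. Placebo subjects sit at concentration zero throughout. A treatment term shifts the level of a group but not its time course. With no time term, a QTcF or HR pattern over the day that is common to both groups has nowhere to go except the residual, the subject effects and the concentration slope.

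The slope and the difference at the highest doses are the model-based results of 7.8.4. Protocol Section 1.3.2.2 gives reaching exposures that could spare a thorough QT trial as one reason for the high doses, so these estimates may be used beyond this study. A shared daily pattern could create an apparent effect or hide a real one.

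**Working it through.** The documents give no figure to reproduce. The check computes what the listed model estimates, in expectation, when the drug has no effect and a daily pattern is shared by all subjects.

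**Inputs from the documents**
- 7 doses, each with 6 active and 2 placebo subjects: 42 active, 14 placebo (Protocol Section 3.1).
- Post-dose ECGs at 0.5, 1, 1.5, 2, 3, 4, 6, 8, 12, 24, 34, 48, 72 and 96 h (SAP Table 6.7: 1). Planned observations: 56 × 14 = 784.
- Half-life 18.6 h (Protocol Section 1.4.3), so λ = ln 2 / 18.6 = 0.0373 per h.
- Predicted Cmax 285 nM at 40 mg, proportional to dose (Protocol Table 1.3.3.1: 1).

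**Assumptions, not in the documents**
- A 24-hour cosine of 2.5 ms semi-amplitude, with the trough at each of 24 clock hours.
- A one-compartment profile with tmax from 1 to 4 h.
- SDs of 4 ms (subject intercept), 1 ms per 100 nM (subject slope) and 6 ms (residual).

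**Formula.** With f the cosine, every subject's expected response is d(t) = f(8:00 + t) minus the mean of f at 7:00, 7:15 and 7:30. With concentration c in units of 100 nM, V = 16J + cc′ + 36I, where J is the all-ones matrix and I the identity. The expected estimate is (ΣX′V⁻¹X)⁻¹ ΣX′V⁻¹d. The difference at a given dose is slope × Cmax + treatment term. As the true effect is zero, every non-zero value is bias.

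**Results without time** (absolute bias; ranges are over tmax; average and worst are over the 24 phases)

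| Quantity | Coding | Average | Worst phase | SE |
|---|---|---|---|---|
| Slope, ms per 100 nM | active/placebo | 0.4–0.8 | 0.7–1.2 | 0.6 |
| Slope, ms per 100 nM | by dose | 0.5–0.9 | 0.8–1.5 | 0.65 |
| 40 mg, ms | active/placebo | 1.0–1.8 | 1.5–2.8 | 2.0 |
| 40 mg, ms | by dose | 0.6–1.2 | 1.0–1.9 | 2.4 |
| 20 mg, ms | active/placebo | 0.4–0.7 | 0.6–1.15 | 1.5 |
| 20 mg, ms | by dose | – | 0.4–0.8 | – |

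At 10 mg the worst phase gives 0.15–0.3 ms (active/placebo). Lower doses reach at most 0.5 ms. Coded by dose, 10 mg and below reach at most 0.4 ms.

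**How the pieces fit** (active/placebo, tmax 4 h, worst phase). The slope bias is 1.19 and the 40 mg bias 2.84, so the treatment term is 2.84 − 1.19 × 2.85 = −0.55. At 20 mg: 1.19 × 1.425 − 0.55 = 1.15. At 10 mg: 1.19 × 0.7125 − 0.55 = 0.30. The bias therefore falls with dose and changes sign near the bottom of the range.

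**With 13 time indicators** the bias is zero, to rounding, in every case.

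**Coverage.** A REML simulation used 600 trials per setting, 30% between-subject PK variability and a random phase. Coverage of the nominal 90% CI at tmax 2 / 3.4 h was:
- Active/placebo: 84.5 / 82% for 40 mg and 75 / 70% for the slope.
- By dose: 87.5 / 86.5% and 76 / 68%.
- With time as a factor: 90–91% throughout.

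At the worst single phase (trough 04:00, tmax 3.4 h), coverage fell to 68% for 40 mg and 51% for the slope (active/placebo), and to 83% and 43% (by dose). At favourable phases it stays near 90%.

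**Other shapes.** SRD flow chart note 3 says "If several actions are indicated at the same time, the intake of meals will be the last action", so ECGs at 4, 24 and 48 h precede the meal. A 5 ms step at the post-meal ECGs (6, 8, 12 and 34 h) gives 0.0–2.0 ms at 40 mg (active/placebo) or 0.0–1.3 ms (by dose), and about zero at tmax 1 h. A second set of assumptions used 5 ms semi-amplitude, SDs of 4, 0.5 and 5, and added a two-compartment profile with AUC0-24/Cmax near 10 h, close to the protocol's 2,850 / 285 = 10. The worst-phase 40 mg bias was 3.6–6.1 ms (active/placebo) and 2.4–3.6 ms (by dose), and again zero with time.

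**The case against.** **The detail section may already contain time.** This is the strongest point. SAP Section 10 is absent from the public text, the SAP places other ECG detail there too, and text withheld in this way is not missing from the plan. The plural in the phrase about fixed categorical effects, with only one factor named, and the time-matched placebo correction in the scatterplot both suggest that the 7.8.4 list may be abbreviated. This stands, and the conclusion is conditional on it. Even so, 7.8.4 gives response, covariates, factor, random effects and estimation method, so it reads as complete and should match 10.1.4.

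**There are safeguards.** Time overlays, residual plots and further models are planned. They could reveal a shared pattern, but further models are triggered only by non-linearity or a delayed effect. The placebo-corrected values are for plotting only. None of this changes the reported slope, differences or intervals unless the model is refitted.

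**The size is assumed, and a time factor costs precision.** This stands in part. Bias is proportional to amplitude. Take the slope with active/placebo coding at tmax 2 h: SE 0.60 without time and 0.60 × 1.14 = 0.68 with it, worst-phase bias 0.79 at 2.5 ms. Averaged over phases, mean squared error at 1 ms is 0.60² + (0.79 × 0.4)²/2 = 0.41 without time, against 0.68² ≈ 0.47 with it, so omission is slightly better. At 2.5 ms it is 0.60² + 0.79²/2 = 0.67 against 0.47, so time is clearly better. The case for time is protection against a swing of unknown size, and intervals that keep their coverage.

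**The consequence is small.** The analysis is exploratory, no primary or secondary endpoint depends on it, and the QT stopping criterion in Protocol Section 3.3.4.3 uses individual confirmed values. This stands and limits the weight of the point.

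**Conclusion.** The concern holds as a conditional one. As listed in 7.8.4, the model does not separate a daily change shared with placebo from the concentration effect. If 10.1.4 adds nominal time, only the list needs completing. If it does not, the reported slope, higher-dose differences and 90% CIs can be biased in either direction.

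At 2.5 ms semi-amplitude the average bias is about 0.7 to 1.4 SE for the slope and 0.25 to 0.9 SE for the 40 mg difference. Multiply the bias by 0.4 for 1 ms and by 2 for 5 ms. At some phases it is near zero.

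The mechanism follows from the documents; the sizes rest on the assumed amplitude, phase, tmax and SDs. Kenward-Roger and the baseline covariate were not reproduced. No separate HR figures were computed, although the same algebra applies. The consequence is modest and the remedy cheap, so the change should be made.

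**What to change.** In SAP Section 7.8.4, name nominal time point as a fixed categorical effect, in addition to treatment, for both the QTcF and the HR model. State how treatment is coded. Check that Section 10.1.4 agrees and add the term there and in the code if it is absent. If the scatterplot regression line comes from this model, take it from the version with time, so that line and placebo-corrected points are on the same footing.

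The cost is one line of text and 14 − 1 = 13 fixed-effect degrees of freedom on 784 planned observations. In the GLS calculation the standard error rises by 7–8% for the 40 mg difference and 14% for the slope (active/placebo), or by 2–3% and 19% (by dose). With 30% between-subject PK variability the increases are 5–6% and 10–12%, or about 2% and 15–16%.
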